2.4 Determination of sample size

No formal sample size computation has been performed for this study. This PK study will be a study of limited size conducted under SD and steady-state conditions to look for sizable differences between adult (18 to 64 years of age) and elderly (≥ 65 years of age) study participants. A total of 28 study participants (10 study participants of age 18 to 64 years and 18 study participants of age ≥ 65 years) is planned.

A sample size of 9 study participants in each age group will have 97% power to detect a fold change in means (expected ratio) of 2.0, assuming that the coefficient of variation is 40% using a 2 group t-test with a 0.05 1-sided significance level.

3 DATA ANALYSIS CONSIDERATIONS

3.1 General presentation of summaries and analyses

Statistical evaluation will be performed by ICON PLC and supervised by the Early Development Statistics Department of UCB. The datasets will follow the UCB analysis data model (ADaM) data specifications. All statistical analyses will be performed using SAS[®] Version 9.4 or later (SAS Institute, Cary, NC, USA).

The PK noncompartmental analysis (NCA) will be performed using Phoenix WinNonlin[®] v6.3 or higher (Certara L.P., Princeton, NJ, USA) for PK parameter estimation using actual doses administered and the actual sampling times relative to time of dose administration.

Categorical endpoints will be summarized using number of study participants (n), frequency, and percentages. Missing data will not be imputed. Individual plasma and urine concentration and PK parameters will be presented using 3 significant digits.

When reporting relative frequencies or other percentage values, the following rules apply:

- For values where all study participants fulfill certain criteria, the percentage value will be displayed as 100
- For values where the absolute frequency is zero, there will be no percentage displayed
- All other percentage displays will use 1 decimal place

Percentages displayed based on continuous data (e.g. percentage changes from baseline) will be displayed to 1 decimal place. Unless otherwise stated, the denominator for the percentages will be based on the number of participants in the respective analysis set.

Continuous variables will be summarized by visit and time point (where applicable) including number of study participants (n), mean, median, standard deviation (sd), minimum, maximum. Geometric coefficient of variation (geoCV), geometric mean and 95% confidence interval (CI) for the geometric mean will also be presented in the descriptive statistics for the plasma concentration and PK parameters for PSL and two metabolites of PSL [REDACTED]). In all outputs the confidence limits will be restricted to the possible values that the variable can take.

When reporting descriptive statistics, the following rules will apply in general except for PK concentration data (plasma and urine PK) of PSL and two metabolites of PSL [REDACTED]:

- n will be an integer
- Mean (arithmetic and geometric), standard deviation and median will use 1 decimal place more, or 1 significant figure more – depending on the reporting format of the original data – than the original data
- Confidence intervals will use 1 decimal place more, or 1 significant figure more – depending on the reporting format of the original data – than the value around which the confidence interval is constructed
- Coefficient of variation (CV) will be reported as a percentage to 1 decimal place
- Minimum and maximum will be reported using the same number of decimal places or significant figures as the original value
- If no participants have data at a given time point, then only n=0 will be presented. If n<3, then only the n, minimum and maximum will be presented. If n=3, then only n, minimum, median and maximum will be presented. The other descriptive statistics will be left blank.

When reporting individual values and descriptive statistics for PK concentration data (plasma and urine PK of PSL and two metabolites of PSL, [REDACTED]), the following rules will apply regarding rounding and precision:

- Individual values for PK concentration data will be reported to the same level of precision as received from the bioanalytical laboratory
- Descriptive statistics for PK concentration data will be reported to the same level of precision as the individual data for the minimum and maximum, and to 1 additional decimal place or 1 additional significant figure – depending on the reporting format of the original data with a maximum of 3 significant digits - for the mean (arithmetic and geometric), median and standard deviation. The 95% CI for the geometric mean will use 1 decimal place more, or 1 significant figure more – depending on the reporting format of the original data – than the value around which the confidence interval is constructed
- Geometric CV will be reported as a percentage to 1 decimal place

When reporting individual values and descriptive statistics for PK parameters (plasma and urine PK of PSL and two metabolites of PSL [REDACTED], and parent to metabolite ratio) the following rules will apply with regard to rounding and precision:

- Individual values for PK parameters will be reported to 3 significant figures
- Descriptive statistics for PK parameters should be rounded to 4 significant figures for the mean, median and standard deviation and to 3 for the others

Data listings containing all documented data and all derived data will be generated and presented by age group (Adults (18-64 years) and Elderly (>=65 years)).

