On Day 22, study participants will complete the EOS/EOT Visit procedures as specified in the Schedule of Activities (Table 1-2).

Dropouts may be replaced at the discretion of the Investigator and Sponsor.

Number of participants

A total of approximately 28 study participants will be enrolled overall in the US (at least 10 adult and at least 18 elderly study participants).

Treatment groups and duration

The maximum study duration for adult and elderly study participants is 50 days (up to 28 days for Screening plus 22 days from Baseline [Day 1] through the EOS/EOT Visit).

This document cannot be used to support any marketing authorization application and any extensions or variations thereof.

REDACTED COPY

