3.5.2 Full Analysis Set

The Full Analysis Set (FAS) consists of all study participants who have signed the ICF and received at least one dose of investigational medicinal product (IMP). Analysis of this set will be according to the treatment the study participants actually received. All safety analyses will be performed using the FAS.

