10 SAFETY ANALYSES

All safety summaries and listings will be performed using the FAS. All safety variables will be summarized by the age group (adult and elderly study participants) and Treatment Period (SD, MD, and overall). Unless stated otherwise, all summaries including figures will be presented as detailed in the shells for figures. Summaries for continuous variables by time points will be based on the averaged value. Categorical variables will be summarized.

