10.2 Adverse events

All AEs will be coded using the MedDRA[®] and characterized as pre-treatment, SD-treatment-emergent and MD-treatment-emergent according to the intake of the study medication.

- Adverse events with a start date prior to the first dose of study medication will be defined as pre-treatment AEs.
- SD-treatment-emergent AE (SD-TEAE) is defined as any AE with a start date/time on or after the first dose of study medication and until Day 7 (last Day of Period 1A) or any unresolved event already present before administration of study medication that worsens in intensity following exposure to the SD-treatment.
- MD-treatment-emergent AE (MD-TEAE) is defined as any AE with a start date/time on or after the first dose of study medication during the Period 1 B (usually on Day 8) and until 168 hours after the last PSL intake or any unresolved event already present before

administration of study medication during Period 1B that worsens in intensity following exposure to the MD-treatment.

Where dates are missing or partially missing, AEs will be assumed to be SD-treatment-emergent and MD-treatment-emergent, unless there is clear evidence to suggest that the AE started prior to the first dose of study medication. Missing or partially missing dates for AEs will be handled as described in [Section 4.2.4](#).

All AEs starting after the first intake of PSL through Day 7 will be attributed to SD-Treatment Emergent AEs; all AEs starting (strict) after Day 7 (the first PSL intake during Period 1B is foreshen on Day 8) through Day 22 will be attributed to MD-Treatment Emergent AEs and AE starting more than 168 hours post last dose of PSL will be attributed to the FU period.

All AEs will be recorded in the Case Report form (CRF) from the time of informed consent until study completion or termination. All AEs will be coded (see [Section 3.8](#)) and categorized by intensity (mild/moderate/severe) and relationship (related/not related) to study drug PSL as judged by the Investigator.

The number and percentage of participants who experience SD-TEAEs and MD-TEAEs will be summarized by MedDRA SOC, PT. The occurrence and incidence of AEs will also be summarized by intensity and relationship to PSL. Adverse events leading to discontinuation and SAEs will also be summarized.

Summaries of TEAEs (SD-TEAEs and MD-TEAEs) will include the following:

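### Multiple-dose safety percentages are divided by the whole FAS, which includes participants who never took a Period 1B dose, and the MD event rules do not consistently keep those participants out of the numerator

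*SAP*

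**What the plan says.** SAP 3.1 sets a default, which holds where nothing else is stated: "the denominator for the percentages will be based on the number of participants in the respective analysis set". SAP 3.5.2 adds "All safety analyses will be performed using the FAS", and SAP 10 repeats this for summaries and listings. One dose in either period qualifies a participant for the FAS. SAP 10 asks for safety results by age group and by period (SD, MD and overall), and SAP 10.2 states: "The number and percentage of participants who experience SD-TEAEs and MD-TEAEs will be summarized by MedDRA SOC, PT". No separate denominator is given for the MD column, and neither document defines a Period 1B safety set. SAP 5.2 also splits important protocol deviations by period, and there it names the FAS as the denominator outright.

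SAP 10.2 decides in three ways what counts as an MD event:
- by dose: onset from the first Period 1B dose until 168 hours after the last dose, or worsening after that first dose;
- by calendar: onset after Day 7 and up to Day 22, with no mention of a Period 1B dose;
- by default: an event with a missing or partial date is taken as both SD- and MD-emergent, unless it clearly began before the first dose.

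On early stopping, Protocol 7.1 rules out any restart of study medication, and the Protocol synopsis says "Dropouts may be replaced at the discretion of the Investigator and Sponsor".

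**The concern.** A participant who takes the Day 1 dose and stops before Day 8 is never exposed to multiple dosing, yet stays in the number that divides the MD counts. The incidence of TEAEs, SAEs and TEAEs leading to discontinuation is the secondary safety endpoint. The study exists to compare adults with the elderly, and the planned cohorts are 10 and 18, so one participant moves a percentage visibly. If early stopping differs between the cohorts, the MD comparison by age shifts for a reason unrelated to what happened on multiple dosing.

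Stopping between the periods is possible under the plan. Participants may leave the site from Day 5 until the evening of Day 7, the drug screen and safety laboratory tests are repeated on Day 8, and anyone who discontinues study medication cannot resume it.

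**Working it through.** **The plan's own figures.** The documents give no expected dropout and no expected event rate, so no stated figure on this point can be reproduced. The only sample-size figure is the PK power statement in SAP 2.4 (97% with 9 per group). It reproduces at 97.7%, but this point does not depend on it.

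**Inputs.** N is 10 adults and 18 elderly (SAP 2.4). k is the number in the FAS with no Period 1B dose; it is an assumption, taken from 0 to 4 per cohort. x is the number of participants with an MD event, first taken to come only from those with a Period 1B dose.

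**Formulas.** Without replacement, the printed percentage is x/N and the at-risk percentage is x/(N−k). Printed divided by at-risk is (N−k)/N. If every loss is replaced, so that N participants take Period 1B doses, the FAS grows to N+k and the ratio is N/(N+k).

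| k | Adults, not replaced | Adults, replaced | Elderly, not replaced | Elderly, replaced |
|---|---|---|---|---|
| 0 | 1 | 1 | 1 | 1 |
| 1 | 9/10 = 0.900 | 10/11 = 0.909 | 17/18 = 0.944 | 18/19 = 0.947 |
| 2 | 8/10 = 0.800 | 10/12 = 0.833 | 16/18 = 0.889 | 18/20 = 0.900 |
| 3 | 7/10 = 0.700 | 10/13 = 0.769 | 15/18 = 0.833 | 18/21 = 0.857 |
| 4 | 6/10 = 0.600 | 10/14 = 0.714 | 14/18 = 0.778 | 18/22 = 0.818 |

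**Effect on the age comparison.** Suppose three elderly participants and no adults stop before Day 8, without replacement, and 60% of those on multiple dosing have an event in each cohort. Adults print as 6/10 = 60%. The elderly rate is 9/15 = 60% among those at risk but prints as 9/18 = 50%. The 10-point difference comes from the denominator alone.

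**The numerator.** For someone dosed only at about 8:00am on Day 1, 168 hours (168/24 = 7 days) ends at about 8:00am on Day 8. An event from the start of Day 8 until then falls to MD under the calendar rule. A later event, up to Day 22, meets both the calendar rule (MD) and the rule in the same sentence of SAP 10.2 that sends events beyond 168 hours after the last dose to follow-up. SAP 10.2 does not say which prevails. An undated event in the same participant is counted as MD in any case. Such entries would push the MD percentage up, against the dilution.

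**The case against.** The SAP 3.1 rule is only a default. SAP 3.5.2 says the FAS is analysed by treatment actually received, and Table 13-1 in SAP 13 lists the two periods under a column headed Treatment. The table shells are not in the documents, so a programmer could reasonably use the number exposed in each period. This is an arguable reading. But neither place states a different N, every participant receives the same drug, and SAP 5.2 applies the FAS to a table split by period. The text as written leads to the FAS.

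It also stands that the endpoint is descriptive and no decision rule hangs on it. An event that causes stopping before Day 8 appears in the SD and overall summaries, discontinuations due to AEs are shown by age group (SAP 5.1), counts accompany percentages, and dosing is listed by participant (SAP 10.1). A careful reader could rebuild the at-risk rate. This limits the harm; it does not make the printed percentage right.

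Three stronger readings might be inferred, and the documents do not support them:
- **Early stoppers can never enter the MD numerator.** The calendar and missing-date rules in SAP 10.2 can place them there.
- **Replacement makes the dilution worse.** For the same k it lessens it: 0.900 against 0.889 in the elderly and 0.833 against 0.800 in adults, at k=2.
- **The rule necessarily flatters the elderly.** The direction depends on k and N in both cohorts. With two losses replaced in each, elderly 6/18 = 33.3% prints as 6/20 = 30.0% and adult 3/10 = 30.0% as 3/12 = 25.0%. The gap widens from 3.3 to 5.0 points, and the elderly look relatively worse.

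**Conclusion.** The point holds. Followed as written, the SAP divides MD participant percentages by everyone dosed on Day 1. Without replacement, each early stopper costs the adult percentage 10% of its value and the elderly percentage 5.6% (1/18); unequal loss can create or hide a difference between the age groups. The factors assume that early stoppers contribute no MD events, which SAP 10.2 does not guarantee, so the net direction in a real table is not fixed in advance.

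The size rests wholly on k, for which the documents give no value; at k=0 there is no effect. Continuous safety summaries report the number of observations and are unaffected. Since the endpoint is descriptive and the counts are shown, this is a definition to settle before database lock and no threat to the primary PK analysis.

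**What to change.** - **Denominator.** In SAP 3.1 and 10.2, state that Period 1B (MD) participant percentages use the FAS participants in the age group who took at least one Period 1B dose, and print that N in the column header. Keep the full FAS for Period 1A and overall.
- **Numerator.** In SAP 10.2, let MD attribution, including the calendar and missing-date rules, apply only to participants with a Period 1B dose. Report later events in the others under overall or follow-up. Make the same change to the MD-concomitant medication definition in SAP 6.4.2, which now runs by calendar from Day 8 to Day 22. Without this step, people could be counted in the numerator and not in the denominator.
- **Tables by time point.** For the vital-sign TEMA/PCS criteria (SAP 10.4.1) and QTcF categories (SAP 10.4.2), divide by the participants with an assessment at that time point.
- **Context.** Show by age group how many stopped before Period 1B.

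The cost is one derived flag, a few sentences and a SAP amendment, which SAP 1 requires when analysis definitions change before database lock. Study conduct is unchanged. There is a small downside: the MD rates will describe only those who went on to multiple dosing, a group partly selected by how they fared after the single dose. The last item lets the reader see that selection.

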3.2 General study level definitions

3.2.1 Relative day

The relative day of an event will be derived with the date of first dose of investigational medicinal product (IMP), here PSL as reference.

Relative days for an event or measurement occurring before the date of first dose of each treatment period are calculated as follows:

$$\text{Relative Day} = \text{Event Date} - \text{Date of First Dose in the treatment period}$$

The relative day for an event or measurement occurring on the date of first dose of each treatment period is 1. The relative day for an event or measurement occurring on or after the reference date to the date of the last dose in the treatment period will be calculated as follows:

$$\text{Relative Day} = (\text{Event Date} - \text{Date of First Dose in the treatment period}) + 1$$

For events or measurements occurring after the date of last dose, relative day will be prefixed with '+' in the data listings and will be calculated as follows:

$$\text{Relative Day} = + (\text{Event Date} - \text{Date of Last Dose in the treatment period})$$

There is no relative Day 0. Relative day will not be calculated for partial dates in cases where relative day is shown in a participant data listing. In such cases, relative day should be presented as '--' in the relevant participant data listing.

3.2.2 Study periods

For each participant completing the study, the expected maximum duration of participation will be approximately 50 days with a maximum of 10 days exposure to investigational product, and will consist of the following periods:

- Screening Period (Day -28 to Day +3)

The Screening Period consists of a single Screening Visit, which will be conducted at the unit within 28 days prior to check-in for Treatment Period, and a Baseline Visit, which will be conducted at the clinical research unit (CRU) 1 day prior to Treatment Period. Study participants will check-in at the CRU on Day -1.

- Treatment Period 1A (PSL SD administration) (Day 1 to Day 7)

In Period 1A study participants will receive a single oral dose of 200mg PSL on Day 1, at approximately 8:00am, 30 minutes after a light meal has finished. No study drug will be administered on Days 2 to 7; assessments will be conducted during this time as specified in the Schedule of Activities ([Table 2-1](#)). Days 2 to 7 are designated as a 6-day washout.

- Treatment Period 1B (PSL MD administration) (Day 8 to Day 21)

In the Period 1B study participants will receive multiple oral PSL doses on Days 8 to 16, followed by a 5-day washout (Days 17 to 21). Padsevonil will be administered BID, with one dose in the morning [approximately 8:00am] and one dose in the evening [approximately 8:00pm]. The specific PSL dosing schedule is as follows:

Day 8: 50mg PSL BID

Day 9: 100mg PSL BID

Days 10 to 12: 200mg PSL BID

Day 13: A morning dose of 200mg PSL and an evening dose of 100mg PSL

Days 14 and 15: 100mg PSL BID

Day 16: 50mg PSL BID

Days 17 to 21: no PSL administration; 5-day washout

- The Follow-Up Period consists of an End of Treatment (EOT) /End of Study (EOS) Visit performed on Day 22 after discharge or upon discontinuation of the study.

The end of the study is defined as the date of the last visit of the last participant in the study.

3.3 Definition of Baseline values

Baseline will be the last non-missing value prior to first PSL dosing in each period (Period 1A (SD) and Period 1B (MD)). Scheduled or unscheduled measurements can be used as the Baseline value.

If a measurement is repeated at Baseline or a given treatment period and is obtained prior to dosing, then the last available measurement will be used as the Baseline value.

12-lead ECG will be measured in triplicate. The mean of the last three predose measurements will be taken as the baseline; if less than three predose replicates are available, the mean of the available predose replicates will be taken as the baseline.

The change from Baseline to any subsequent post-Baseline visit will be calculated as the simple difference between that post-Baseline visit's value and the Baseline visit value, as below:

$$\text{Change_from_Baseline} = \text{Post Baseline Visit Value} - \text{Baseline Visit Value}$$

3.5 Analysis sets

3.5.1 All Study Participants

All Study Participants consist of all study participants who have signed the Informed Consent form (ICF).

3.5.2 Full Analysis Set

The Full Analysis Set (FAS) consists of all study participants who have signed the ICF and received at least one dose of investigational medicinal product (IMP). Analysis of this set will be according to the treatment the study participants actually received. All safety analyses will be performed using the FAS.

3.5.3 Pharmacokinetic-Per Protocol Set

The Pharmacokinetic-Per Protocol Set (PK-PPS) is a subset of the FAS, consisting of those study participants who had no important protocol deviations affecting the PK parameters and had a sufficient number of samples available to determine at least one PK parameter.

All PK analyses will be performed using the PK-PPS.

3.6 Treatment assignment

Tables will be presented by age group (Adults (18-64 years) or Elderly (≥ 65 years)) and overall. Listings will be presented by age group and study period as described in Section 3.2.2. PK summaries will be presented for PSL and two metabolites of PSL during the treatment periods (SD and MD)

Table 3–2: Padsevonil administration

Cohort A (adults; n=at least 10) and Cohort B (elderly; n=at least 18)																		
Treatment Period																	Follow-up Period	
Period 1A (SD)							Period 1B (MD)										EOS/EOT Visit	
Day	1	2	3	4	5 to 7	8	9	10	11	12	13 morning	13 evening	14	15	16	17 to 21	22	
	Washout															Washout		
PSL Dose (mg)	200					50 BID	100 BID	200 BID	200 BID	200 BID	200	100	100 BID	100 BID	50 BID			
	Plasma	Plasma	Plasma	Plasma							Plasma							
	Urine	Urine	Urine	Urine							Urine							

BID=twice daily; EOS=End-of-Study; EOT=End-of-Treatment; MD=multiple dose; PK=pharmacokinetic(s); PSL=padsevonil; SD=single dose

Note: BID dosing will be at approximately 8:00am and 8:00pm.

Note: To allow age-dependent effects, elderly study participants will include preferably the following categories: at least 3 males and 3 females from ≥65 to 74 years old and at least 3 males and 3 females ≥75 years old. The elderly study participants will be analyzed as one group. If an effect of age category is observed on PK or safety parameters, the effect of the age category will be explored.

This document cannot be used to support any marketing authorization application and any extensions or variations thereof.

REDACTED COPY

